APPENDIX XIII

Patient Questionnaire

Protocol No: CRO-2025-09-WHT-MS	U.S./0
APPENDIX XIII Patient Questionnaire Study CRO-2025-09-WHT-MS Product Code :	U.S. IRS OCT - 7 2025 POVED"
ID#:	
 Questionnaire for the Patient Receiving the Treatment Baseline: Take a look at your teeth before treatment starts without the gingival barrier. 	
 After 3rd Treatment (Gingival Barrier and Cheek Removed) - to be filled out by the pathenselves 	patient
 Did you notice your teeth got whiter after the 3rd treatment? (circle one) Yes No 	
 Did you experience any sensitivity? (circle one) Yes - (a Little, a Moderate amount, a Lot) - if yes, circle how much No - skip to Q3 	
2a. Where did you experience the sensitivity? Circle all that apply Teeth Gums Other (specify):)	
3. Did you find the entire experience comfortable? (circle one) Yes No - please indicate what was not comfortable about the experience?	
• After 1 Week to be filled out by the patient	
 Are you happy with the whitening results after 1 week? (circle one) Yes No 	
2. Do you have any prolonged sensitivity? (circle one) Yes No	
3. Would you recommend this treatment to a friend/family? (circle one) Yes No	

3a. Why or why not?

U.S. IRA

OCT - 7 2025

APPROVED"

Study	CRO-2025-09-WHT-MS
0.50	

Product Code : _____
ID#:

Questionnaire for the Dental Professional Administering the Treatment

• After 3rd Treatment

1. Are you happy with the patients' whitening results after the 3rd treatment? (circle one)

Yes

No

2. How would you describe the overall process? (circle all that apply)

Quick and easy

Easy to understand how to use

Easier to use than other in-office whitening systems

Questionnaire for the Dental Professional Administering the Treatment

After 1 Week

1. Are you happy with the patient's whitening results after 1 week? (circle one)

Yes

No

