All subjects will be evaluated visually for tooth color shades and conditions of oral tissues at the screening visit. If qualified, subjects will be enrolled and randomized into the study. Baseline visit will be performed on the same day, if time allows. All voluntary candidates will be evaluated for tooth color shades at study entry and the initial tooth shade scores will be recorded as baseline. All qualified subjects will be randomly assigned following a computer-generated master randomization list (online software Sealed Envelope Ltd v.2022) to one of the four treatment groups. Subjects will undergo in-office whitening treatment according to their assigned group. Afterwards, subjects will again have their tooth shade evaluated and recorded, and will be given instructions and hygiene products to use at home, and dismissed. In a subset of subjects (approximately 5/cell), extraoral photos will be taken prior to product application, and after all whitening sessions are completed.

The subjects will be asked to return to the clinic after 1 week, and will again be evaluated for tooth shade, conditions of oral tissues and the occurrence of adverse reactions. Images will again be taken, and a brief questionnaire will be completed to document the patient's experience. After this point, the subject will be dismissed from the study.

3. Master Randomization Plan

Qualifying participants (enrolled) will be randomized using an online software provided by Sealed Envelope Ltd. v.2022. This software employs a block randomization approach with a block size of 6 to ensure balanced allocation to the treatment groups. The randomization sequence will be pre-generated using the 'Create a blocked randomization list' tool. The computer-generated Master Randomization List, which contains random product codes, will be provided to the clinical site prior to the initiation of the study.

Protocol No: CRO-2 Table I. Study		MS	U.S. IRE OCT - 7 2025 *APROVED"
	Visit 1a	Visit 1b	Visit 2
Visit Procedure	Screening/ Baseline	Immediately after treatment	Day 7
Informed Consent Form/ Privacy Notice	х		
Medical History/Oral Health Questionnaire	Х		
Visit Form			x
Review Selection Criteria	Х		
Oral Soft and Hard Tissue Assessment	X	X	X
On-site brushing*	Х	X	X
Tooth Color Exam (Visual grading)	X	x	X
Photos (in subset only)	X	X	x
In-office whitening	х		
Questionnaire	х	X	X
Randomization, product assignment and instructions	X		

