The Vita Extended Bleachedguide 3D-Master includes 29 tabs arranged and numbered by the manufacturer from 1 to 29 (lightest to darkest). Both sets of tabs will be used to assign a shade score to each maxillary anterior tooth. All maxillary anterior teeth must each have a minimum score of a 17 according to the Vita Extended Bleachedguide 3D-Master. Individual tooth shade scores will be recorded on the Tooth Color Examination Form (Appendix VIII).

The methods employed for tooth shade assessments are outlined in Appendix I (Tooth Shade Assessment Guidelines).

5. Extraoral Photos

In a subset of subjects (approximately 5/cell), extraoral photos will be taken using a handheld SmileLite MDP2 system with an attached smartphone. The patient's position will be kept as consistent as possible. Photos will be taken prior to product application, with the retractor in place and no gingival barrier, and will be repeated once more after all sessions are completed and the gingival barrier is removed (again with the retractor in place).

6. Randomization and In-office Whitening

Study subjects will be randomly assigned to one of the three (3) study groups. In-office whitening will then be performed according to the product instructions. This procedure will vary depending on which group the subject is assigned to. An overview of application guidelines for each product is included in Appendix XII.

7. Questionnaire

Subject and provider will complete the relevant portions of a short questionnaire.

Visit 1b: Immediately post-whitening:

1. Oral Soft and Hard Tissue Assessment

All subjects will receive a visual evaluation of their oral soft and hard tissues. This examination will be performed by a study dentist and will include an evaluation of the lips, soft and hard palate, gingival mucosa, buccal mucosa, mucogingival fold areas, tongue, sublingual and submandibular areas, salivary glands, the tonsilar and pharyngeal areas, and teeth. The results of this evaluation will be recorded on the Oral Soft and Hard Tissue Assessment Form (Appendix VII).

U.S.IRB

OCT - 7 2025

On-site brushing

Subjects will again be asked to perform a supervised on-site brushing with water for 2 minutes. Afterwards, they will be instructed to rinse with water thoroughly. Shade examination should be done approximately 5 minutes after rinsing, to allow for re-hydration of the tooth surface.

3. Tooth Shade Assessment

The methods employed for tooth shade assessments will be repeated.

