The primary outcome variable of this study will be tooth shade whitening improvements via the Vita Extended BleachedGuide 3D-Master (29 tabs).

Demographics

A Chi-Square test will be performed on the gender demographic data to test the hypothesis that the Treatment groups are stratified and balanced with respect to gender. In addition, an analysis of variance (ANOVA) will be performed on the age demographic data to test the hypothesis that the mean age of the treatment groups are balanced with respect to age.

Outcome variables [Vita Extended Bleachedguide 3D-Master® (29 tabs)]

Shade changes between the baseline and each follow-up examination will be quantified by taking the difference in shade rank scores (where a positive difference is indicative of a lightening of the tooth, for example). Both the shade rank scores for each examination and the shifts in rank scores between examinations will be summarized for each subject by taking the mean across all measured teeth. Comparisons among the study treatment groups will be based upon an analysis of these mean scores.

Within Treatment Analysis

Within-treatment group comparisons between the baseline and post-treatment shade scores will be analyzed using a paired t-test. All statistical tests will be two-sided and employ a level of significance at the α = 0.05.

Between Treatment Analysis

For the primary outcome variable, the shade change scores from baseline will be analyzed using an analysis of covariance (ANCOVA) model with treatment as a factor and the baseline shade scores as a covariate to compare the study treatment groups. Age and gender will be included as a covariate in the model, if they are determined to be statistically significant at baseline. P-values for the treatment group shade change comparisons, adjusted means

treatment group shade change differences and their 95% confidence intervals will be provided at all time points. All statistical test of hypotheses will be two-sided and employ a level of significance of α = 0.05.

VIII. SUBJECT RECORD FORMS

The following subject record forms will be completed by the study investigators according to the following schedule:

Visit 1a (Screening/Baseline):

Informed Consent Form/Privacy Notice Photo Release Form Medical History/Oral Health Questionnaire Initial Screening Form Oral Soft and Hard Tissue Assessment Form Tooth Color Assessment Form Questionnaire

Visit 1b (Immediately after whitening)

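### The provider's ease-of-use question offers only favourable answers, which makes it a one-sided and weak basis for comparing the three systems

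*Combined protocol and SAP*

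**What the plan says.** Section V, Visit 1b, item 5 states: "Subject and provider will complete the relevant portions of a short questionnaire". Table I schedules the questionnaire at all three time points, and Section VIII lists it among the subject record forms.

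The provider's part of Appendix XIII has two items after the third treatment. The first is a Yes/No item: "Are you happy with the patients' whitening results after the 3rd treatment? (circle one". The second is "How would you describe the overall process? (circle all that apply", followed by three options:

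- "Quick and easy"
- "Easy to understand how to use"
- "Easier to use than other in-office whitening systems"

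No other option and no free-text line is printed. The page carries a product code and a subject ID.

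On purpose, Section III.2 says of the one-week visit that "a brief questionnaire will be completed to document the patient's experience". Section VII states: "The primary outcome variable of this study will be tooth shade whitening improvements via the Vita Extended BleachedGuide 3D-Master (29 tabs". It gives no analysis of the questionnaire, no usability endpoint and no rule for blank items.

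**The concern.** The three options differ in content but not in direction. A provider who found a system slow, hard to follow or harder than its rivals has nothing to circle. Leaving the item blank is the only way to withhold praise, and that looks the same as overlooking it.

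Two features make this worse. The third option asks for a comparison with unnamed other systems. A provider rating the test system judges it against one set of alternatives, and a provider rating either control judges against a different set. Also, the trial is blinded only for the examiner. The three procedures in Appendix XII differ visibly, so the person applying the product knows which system is in use, and the leading wording is put to an unblinded rater.

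At stake is the meaning of any ease-of-use percentage taken from this form. The title-page material describes a claims study, and the objective is comparison with marketed systems, so such a percentage could be reported. As the item stands, the percentage would have no clear complement.

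**Working it through.** The plan states no rate, sample size or power for this item, so there is no figure to reproduce. Four checks follow.

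**1. Direction of the options (Appendix XIII).** Favourable: 3 of 3. Neutral: 0. Unfavourable: 0. None of these: absent. The other evaluative items on the form do allow an unfavourable answer. Both provider items on whitening results are Yes/No. The patient comfort item has a No with a reason. The sensitivity item records degree and site. The recommendation item asks why or why not. Only the usability item has no negative answer.

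**2. Possible responses.** Three options that may each be circled give 2³ = 8 patterns: 7 non-empty, all favourable, and 1 blank with two meanings.

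**3. Effect of the ambiguous blank (assumed rates).** If a true proportion p would endorse an option, a fraction s skip the item, and blanks count as not endorsed, then observed = p × (1 − s). With p = 0.80:

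- s = 0.05: 0.80 × 0.95 = 0.76
- s = 0.10: 0.80 × 0.90 = 0.72
- s = 0.20: 0.80 × 0.80 = 0.64

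The same point in counts, also assumed: in an arm of 60, 40 forms have something circled and 20 are blank. If k of the 20 blanks were skipped, the share among those who answered is 40/(60 − k). That is 40/60 = 67% for k = 0, 40/52 = 77% for k = 8, and 40/40 = 100% for k = 20. The form does not show which applies.

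**4. Is a comparison by arm possible at all?** The product code allows answers to be grouped by system. Inputs: 60 per arm (Synopsis); 54 per arm after the 10% drop-out in Section II (60 × 0.9); two-sided α = 0.05 (Section VII); endorsement rates assumed. With p̄ = (p₁ + p₂)/2,

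power = Φ{ [|p₁ − p₂| − 1.96 √(2p̄(1 − p̄)/n)] / √([p₁(1 − p₁) + p₂(1 − p₂)]/n) }.

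For 90% against 70% with n = 60: p̄ = 0.80; 1.96 × √(0.32/60) = 0.143; √(0.30/60) = 0.0707; (0.200 − 0.143)/0.0707 ≈ 0.80; power ≈ 0.79.

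| Assumed rates | n = 60 | n = 54 |
|---|---|---|
| 90% vs 70% | 0.79 | 0.75 |
| 80% vs 60% | 0.67 | 0.62 |
| 80% vs 50% | 0.94 | 0.92 |

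These are best-case figures. They treat answers as independent, although one provider may answer for many subjects, and they ignore the blanks in step 3. They show that a comparison of endorsement rates is possible in principle, not that it would be sound.

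**The case against.** The strongest reply is that no planned result depends on this item. Shade is the primary outcome, Section VII does not analyse the questionnaire, and the title-page material ties the claims to whitening efficacy. That stands: the shade analysis, sample size and alpha are untouched, and use of the item for a usability claim is a possibility that the documents do not state.

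A reader might infer that the item cannot support any comparison between systems. The documents do not bear that out. The options are the same in every arm, failing to circle one carries some information, and the product code allows tabulation by arm.

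A reader might also infer that unfavourable experience is lost altogether. It is not. The items listed under step 1 of the working capture dissatisfaction with results, discomfort and sensitivity. Only operator difficulty has no negative response.

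A further reply is that question 1 helps to interpret a blank: if it is answered and question 2 is empty, the provider probably meant that nothing applied. This narrows the ambiguity but does not remove it, because a provider can answer one item and miss the next.

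Finally, the number of ratings should not be taken as 180. The item is headed as following the third treatment, and the Appendix XII guidance for the 40% gel makes repeat applications conditional, up to three. Some subjects may not reach that point.

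**Conclusion.** The point holds in a limited form. Question 2 cannot actively record a poor usability rating, its blank has two meanings, and its comparative option has a reference that shifts with the arm. It is a one-sided, weak basis for comparing the systems, though endorsement of each option can be tabulated by arm.

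The direction count (3 of 3 favourable) comes straight from the form and should be confirmed against the copy issued to the site. The fall from 80% to between 76% and 64% rests on assumed endorsement and skipping rates. The consequence is minor: it arises only if ease-of-use results are reported or used in a claim, and it does not touch the primary shade analysis.

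**What to change.** Before the form is used, replace question 2 with balanced single-answer items, worded identically in all three arms:

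- ease of the process, on a scale from difficult to easy;
- ease relative to other in-office systems the provider has used: harder, same, easier, or no basis to compare.

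At minimum, keep the present options and add matching unfavourable ones and a none-of-these choice. In either case, add a completeness check when the form is collected, so that a blank is known to be missing. A forced electronic entry should not be assumed, because Section VIII does not list the questionnaire among the items captured on eCRFs.

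If forms have already been completed on the current page, the unfavourable answers that it could not take are not recoverable. Those data should be reported as descriptive only and kept apart from answers on the revised item.

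Cost: one questionnaire page. Section XII (Protocol Compliance) requires a written amendment agreed by sponsor and investigator and approved by the IRB before implementation, so notification alone is not enough. No visit, staff or procedure is added. The reported ease-of-use figures may be less favourable.
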